Hypothesis: Participants in the rTMS group (Experimental group) compared to the sham treatment group (Control group) will have statistically significantly improvement on the: (a) Davidson Trauma Scale (DTS) (b) the Pittsburgh Sleep Quality Index(PSQI), theEpworth Sleepiness scale (EPS), and sleep polysomnogram (PSG) measures and (c) Cognitive domains including global cognitive functioning, memory, attention and executive function at the end of the active treatment period (i.e., after 20 sessions) and during the follow-up period (i.e., weeks 8, 12, and 16).

Variables:

Posttraumatic Stress Disorder: The Davidson Trauma Scale (DTS)¹⁰⁰ will be administered to measure severity of post-traumatic stress disorder. This is a 17-item self-report scale. The frequency and severity of symptoms are reported on a 4 point scale (0=not at all; 4= everyday); distress is also rated on a 4 point scale with higher scores indicating more severe distress. The scale is valid, with high internal consistency ¹⁰¹. The PTSD variable will be the total score on the DTS.

Subjective Measurement of Sleep Disturbance: Two different subjective sleep scales will be administered at the initial and all follow-up visits. At the initial visit, subjects will also be interviewed for their pre-TBI sleep status. The Epworth Sleepiness Scale¹⁰² is a well validated scale to assess daytime sleepiness. The Pittsburgh Sleep Quality Index (PSQI)¹⁰³ is a self-report questionnaire that examines sleep quality and disturbances in adults. It has been shown to be a valid and useful sleep disturbance screening measure for patients with TBI¹⁰⁴.

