Objective Measures of Sleep Disturbances: Polysomnogram (PSG): Subjects' willingness to have sleep studies will be evaluated at the time of the initial evaluation, and only those willing will be enrolled in the study. For PSGs, participants will be admitted to the Johns Hopkins Bayview Clinical Research Unit, which is a component of an Institutional Clinical Translations Research program, for 2 overnight sleep studies (initial study at baselineand second study at week 16).. At both of these timepoints, subjects will undergo standard PSGs on 2 consecutive nights. The first PSG will be conducted for adaptation purposes. Only data from the second night will be used in data analyses. In summary, there will be a total of 4 PSGs, two pre and 2 post treatment. At both these times, the first night is adaptation night and data will not be used in statistical analyses. Data from the second night will be used in statistical analyses

EEG montages used in PSGs will include 6 EEG channels. These will include frontal, central, and temporal electrodes with a non-mastoid linked reference to minimize non-homogeneous current flow and possible misinterpretation of asymmetry data. In addition, right and left electro-oculograms will be linked to a single mastoid reference (EOGs), and 3 EMGs will be collected, including a bipolar submental EMG, and 2 bipolar tibial EMGs and an EKG. Respiratory function will be measured via a nasal pressure transducer & oral-nasal airflow thermocouple, pulse oximetry and piezoelectric abdominal and thoracic strain gauges. Periodic leg movement (PLM) measures will also be collected. Registered PSG technicians responsible for recording and scoring polysomnograms will be blinded to study hypotheses. Primary sleep PSG measures of interest include: sleep latency, total sleep time, time spent in each sleep stage, wake after sleep onset time, sleep efficiency, periodic limb movements/hr, and Apnea-Hypopnea Index.

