Neuropsychological Tests: All subjects will complete neuropsychological testing at two time points: during the baseline visit and at the 3-month follow-up visit. The test battery will be constructed to allow evaluation of multiple domains of cognitive functioning, including global cognitive functioning, executive functioning, attention, and memory (Table 6). Briefly, the raw scores on all cognitive measures will be converted to scaled scores using the cumulative frequency distribution of each measure. Scaled scores will then be regressed on age, gender, race, years of education, and estimated premorbid IQ based on the revised National Adult Reading Test (NART)^{105,106} . No additional control for education is necessary.

Table 6: Neuropsychological Tests

Montreal Cognitive Assessment	Test of global cognitive functioning
Wechsler Test of Adult Reading (WTAR)	Pre-morbid Intelligence
Trails B	Test of Executive functioning
Controlled Oral Word Association Test (COWAT)	Test of Executive functioning
Wisconsin Card Sorting test (WCST)	Test of Executive Functioning
Stroop Test	Test of Executive Functioning
Brief test of Attention (BTA)	Test of auditory attention
Trails A	Test of visual attention
Hopkins Verbal learning test (HVLT)	Verbal Memory Test
Brief Visual Memory Test (BVMT)	Visual Memory Test

Behavior Problems: The Neurobehavioral Rating Scale—Revised (NBRs-R) will be used to measure behavioral disturbances following TBI. The NBRs-R is a clinician-based multidimensional instrument and has been validated as a secondary outcome measure to assess behavior problems after brain injury¹⁰⁷.

Secondary Efficacy Measures: DTS; PSQI, EPS, PSG and cognitive measures.

Statistical Analysis: Analyses will be similar to Aim1. Random effects model will be used to compare of the slopes of the LFR rTMS (Experimental group) versus the sham treatment group (Control group) on the Davidson Trauma Scale scores. Random effects models will also be used to compare the two groups over time, controlling for baseline variables found to be statistically significant between the two groups, and the coefficients of interest, such as the interaction between time and treatment assignment.

This same statistical analysis approach will be used to compare the two groups on the sleep scales (PSQI & EPS) and on the primary PSG sleep variables, global cognitive functioning and memory, attention and executive functioning.

Exploratory Analyses:

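### Polysomnography and cognition are hypothesised to improve at four post-baseline times but measured at only one, week 16, so the end-of-treatment, week 8 and week 12 claims cannot be tested for these measures

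*Combined protocol and SAP*

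**What the plan says.** Section 6 (Study Statistics), Secondary Objective, gives one hypothesis for all secondary outcomes. It covers the Davidson Trauma Scale (DTS), the Pittsburgh Sleep Quality Index (PSQI), the Epworth scale, "and sleep polysomnogram (PSG) measures and (c) Cognitive domains including global cognitive functioning, memory, attention and executive function". One timing clause closes the list and applies to all of it: superiority is expected "at the end of the active treatment period (i.e., after 20 sessions") and "during the follow-up period (i.e., weeks 8, 12, and 16"). No outcome is exempted.

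The measurement schedules come a few paragraphs later. Under Objective Measures of Sleep Disturbances, PSG consists of "2 overnight sleep studies (initial study at baselineand second study at week 16"). Each study is two nights, and only the second night is analysed. Under Neuropsychological Tests, cognition is assessed "during the baseline visit and at the 3-month follow-up visit".

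For the analysis, the Statistical Analysis paragraph of the secondary objective sets out a random effects comparison of slopes for the DTS, with the time-by-treatment term as a coefficient of interest. It then extends this: "This same statistical analysis approach will be used to compare the two groups on the sleep scales", the main PSG variables and the cognitive domains.

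Two general statements also make no exception. The Study Design paragraph of the Abstract says the psychiatric and cognitive assessments will be compared at every visit. General Description item c of Section 6 plans plots of the outcome scores at five visits.

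**The concern.** The hypothesis names times at which nobody will have a PSG or a cognitive test. The most important gap is end of treatment, when an effect of the 20 sessions would first be looked for. The only post-baseline data on these measures come 12 weeks after the last session. A null result there cannot separate no effect from an effect that had faded, and a positive result cannot show when the benefit arose. Sleep disturbance and cognitive deficits are two of the three components of Aim 2, so the reporting will matter.

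The analysis is also written for outcomes with several follow-up values. Slope and over-time language applied to one post-baseline value promises a trajectory that the data cannot supply.

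**Working it through.** **1. When is the 3-month follow-up visit?** Study Overview and Study Visits (Section 4) place treatment in weeks 1 to 4 and the three monthly follow-up visits at weeks 8, 12 and 16. The third is week 16, and 16 − 4 = 12 weeks after treatment ends. The Informed Consent subsection lists follow-up at 4, 8 and 12 weeks, which agrees if counted from the end of treatment. If the visit were instead read as study week 12, cognition would still have one post-baseline measurement.

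**2. Hypothesised against measured times.**

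| Outcome | End of treatment | Week 8 | Week 12 | Week 16 |
|---|---|---|---|---|
| PSG, hypothesised | yes | yes | yes | yes |
| PSG, measured | no | no | no | yes |
| Cognition, hypothesised | yes | yes | yes | yes |
| Cognition, measured | no | no | no | yes |

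For each family, 3 of 4 times (75%) are unmeasured. Together that is 6 of 8 cells, or 15 of 20 if PSG is counted with the four cognitive domains separately.

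**3. Share of the whole secondary hypothesis.** Assume that DTS, PSQI and Epworth are rated at all four times. Then the unmeasured share is:
- 6 of 20 (30%) by five outcome families;
- 15 of 32 (47%) with cognitive domains separate;
- 48 of 76 (63%) if the 7 PSG variables and 9 cognitive tests (the premorbid reading test excluded) are counted singly: (7 + 9) × 3 = 48 and (3 + 7 + 9) × 4 = 76.

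The figure depends on the counting rule. Only the 3 of 4 for PSG and cognition does not.

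**4. What the planned model yields with two visits.** Two visits give three within-person covariance quantities: two variances and one covariance. A random-intercept model uses two parameters (intercept variance and residual variance) and can be estimated. Its time-by-arm coefficient is the between-arm difference in mean change from baseline to week 16. The usual random-slope model adds a slope variance and an intercept-slope covariance, making four parameters against three quantities. Slope variation then cannot be separated from residual error.

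**5. Efficiency of that contrast.** Take n per arm, common variance σ² at both visits and baseline-to-week-16 correlation r. Ignore the small cost of estimating the covariate coefficients.
- Change score: variance of the arm difference = (2/n) × 2σ²(1 − r).
- ANCOVA: variance = (2/n) × σ²(1 − r²).
- Ratio = (1 − r²) / [2(1 − r)] = (1 + r)/2.
- At r = 0.5: 0.75/1.00 = 0.75. At r = 0.7: 0.51/0.60 = 0.85.

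The documents give no value of r, so 0.5 and 0.7 are assumptions. The ratio is below 1 for any r below 1. It compares two estimates of the same week 16 contrast and does not measure the loss from the three absent times.

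**The case against.** The best defence is that one general hypothesis sentence was written more broadly than two explicit schedules, and that the schedules are reasonable. Each PSG time point takes two nights, and the trial is a 30-person pilot. That stands: one post-treatment assessment is defensible, and the schedule need not change. It does not rescue the wording, because no other text supplies the missing measurements.

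Three stronger readings are tempting, and the documents do not support them.

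- A reader might infer that the planned model is not identifiable. The plan calls for random effects models with a slope comparison but never specifies subject-level random slopes. With a random intercept the time-by-arm term is estimable and is a valid randomised contrast. The fair criticism is that the random effects structure is unstated and that slope language does not suit two visits.
- A reader might infer that the design cannot answer a stated aim. Aim 2 and the secondary objective name no time points. The four times appear in the hypothesis, and the aim is still addressed at week 16.
- A reader might infer that most of the entire secondary hypothesis is untestable. By family or domain the share is 30% to 47% under the assumption in the working, and the DTS, PSQI and Epworth parts are untouched by these two schedules.

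Nor should one assume that those three scales are documented at every visit. PSQI and Epworth are placed at the initial and follow-up visits, and the outcome description of the DTS gives no schedule. Their end-of-treatment rating rests on the general five-visit statement.

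Finally, preferring ANCOVA is a matter of efficiency, separate from the contradiction in timing.

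**Conclusion.** The concern holds for PSG and cognition only. Three of four hypothesised times, including end of treatment, cannot be tested for these measures. This is explicit for PSG; for cognition it follows from the visit calendar and would be the same count if the visit fell at week 12. The planned slope analysis is valid but reduces to a change-score difference at week 16. ANCOVA would estimate that contrast with 15% to 25% less variance under the assumed correlations and equal variances. The primary outcomes and the sample size are not affected. This should be corrected before analysis, because otherwise a week 16 null may be reported as absence of any effect, including an acute one.

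**What to change.** Reconcile the Abstract's Study Design paragraph, General Description item c, the secondary hypothesis, the PSG and neuropsychological schedules, and the secondary Statistical Analysis paragraph, as follows.

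- Restate the PSG and cognition hypotheses as a between-arm difference at week 16, described as 12 weeks after the last session.
- Analyse each measure by ANCOVA of the week 16 value on arm, baseline value and the time-since-injury stratum used in randomisation. The plan already uses t-tests and linear regression for DTI, which has the same two-point schedule.
- State how subjects without a week 16 value enter the intention-to-treat analysis. Multiple imputation is already named in General Description item b.
- Keep repeated-measures models for scales rated at several follow-up visits, and state the rating times of the DTS, PSQI and Epworth explicitly.
- Commit to reporting a null as no demonstrated effect at week 16, not as no acute effect.

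The cost is protocol and analysis wording, with no added procedure. The downside is that the end-of-treatment, week 8 and week 12 claims are dropped for these measures. Keeping the end-of-treatment claim would need an assessment at that time: adding one increases burden, and moving the existing one gives up the week 16 data.

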Specific Aim 2: To determine the effectiveness of LFR rTMS for the treatment of neuropsychiatric symptoms that are commonly seen as co-morbid phenomena in patients with post-TBI depression: (a) post traumatic stress disorder (PTSD) (b) sleep disturbance and (c) cognitive deficits. We hypothesize that LFR rTMS will be superior to sham treatment in reducing symptoms of PTSD, sleep disturbance and cognitive deficits, more specifically, memory, attention and executive function deficits. In addition, effectiveness of rTMS for the treatment of other behavioral symptoms (e.g. apathy, aggression) will be assessed.

Exploratory Analysis: A subset of subjects will be assessed using diffusion tensor imaging (DTI) to determine white matter integrity pre- and post-treatment in an effort to better understand neuro-anatomical correlates of NPS symptoms, symptom improvement, and the potential for LFR rTMS to influence white matter integrity.

Study Design: The study design will include a double-blind placebo-controlled trial of 30 TBI patients of mild & moderate severities. Subjects will be randomized to either active LFR rTMS (N=15) or sham treatment (N=15). All subjects will receive 20 LFR rTMS or sham treatments over 4 weeks, and will be followed thereafter for 3 months. Well-validated psychiatric instruments and cognitive assessments will be

used to compare the effectiveness of LFR rTMS versus sham treatment cross-sectionally at each of the visits and over time.

Relevance: If the proposed rTMS treatment is found to be efficacious, it can be transferred to clinical practice for soldiers with TBI-associated depression and other psychiatric symptoms. rTMS has minimal long-term side effects and is not known to negatively interact with pharmacotherapies. rTMS has the potential to have a broad impact on multiple areas of life functioning and, thus, has the potential to lead to improved instrumental life activities, employability, community re-integration and overall quality of life. Soldiers & civilians with increased emotional stability and improved cognitive skills can more effectively manage stress which, in turn, can dramatically reduce the likelihood of developing disorders associated with chronic stress.

2. Objectives

The overarching goal of this proposed proof of concept study is to determine the effectiveness of low frequency right (LFR) rTMS for the treatment of post-TBI depression and co-morbid psychiatric symptoms.

SPECIFIC AIMS & HYPOTHESES

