There is no Food and Drug Administration (FDA) approved drug for the treatment of TBI-related NPS symptoms/syndromes. There are only two controlled medication trials in TBI-associated depression, and neither provided strong evidence that antidepressants are superior to placebo. A major limitation of previous studies has been their focus on limited symptoms and use of agents with narrow therapeutic profiles. We propose to address some of these limitations by use of a novel non-invasive technique, LFR rTMS, that has the potential to induce widespread neuromodulation.

Justification and safety information if FDA approved drugs will be administered for non-FDA approved indications or if doses or routes of administration or participant populations are changed. NA

Justification and safety information if non-FDA approved drugs without an IND will be administered. NA. We anticipate that the Johns Hopkins IRB will classify our trial as significant risk, in which case we will require an IDE from the FDA.

6. Study Statistics

General Description

- a. Definition and selection of dataset: Intention-to-treat (ITT) will include all subjects who are randomized to participate in the protocol. The per-protocol (PP) population will include all subjects in the ITT population who meet the additional criteria of no major protocol violations and compliance with study treatment. Baseline demographic and clinical features, including medical comorbidity, pain, fatigue, and post-concussive symptoms will be included in the ITT dataset. Effect assessment will be included in both the ITT and PP dataset.
- b. Basic exploratory analyses will first be conducted, including checking of distributional assumptions, assessment of relationships among covariates, and missing-value multiple imputations.
- c. Continuous variables will be described using means, standard deviations, medians, minimums and maximums, and 95% confidence intervals for parameter estimation. Graphical display (spaghetti plots) of the outcome scores will also be generated for 5 visits (baseline, end of 20 LFR rTMS sessions, week 8,12, and 16) by group. Category and count variables will be described using frequency or proportions.
- d. Analyses will be conducted using STATA 11.2 (StataCorp, Texas, 2009) or R 2.13.2 (2011). All statistical tests will be judged for significance based upon a two-sided p-value of less than 0.05.

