Fatigue: The Fatigue Severity Scale¹¹¹ will be used to assess the severity of fatigue. It has been used both clinically and for research applications, and has been used in the assessment of fatigue in neurological and non-neurological conditions.

Post-Concussive Symptoms: As a myriad of post-concussive symptoms are present after TBI, the Rivermead Postconcussive Questionnaire¹¹² will be used to determine post-concussive symptoms and calculate the total score.

Power Analysis:

The power calculation for this study is based on the study by Fann et al⁴⁵ and our clinical experience. In the open labeled study of sertraline (Zoloft) for the treatment of TBI depression, Fann et al found a response rate (decrease in Hamilton depression scale score of > or = 50%) of 87% and remission rate (Hamilton depression scale score of < or = 7 at the end of treatment) of 67%. Based on these results, we hypothesize improvement in symptoms on the HAMD of 60-70% in the experimental group; and based on our clinical experience, we hypothesize a remission rate of 10% in the Control group. The table (Table 7) below depicts sample sizes for these remission rates with various degrees of power. As this is a pilot study, we have chosen a sample size (N=30) that is feasible and that will allow us to complete the study in the allocated time. Results from this study will help us to develop future studies with larger sample sizes and more conservative numbers. Sample size was calculated with (StataCorp, Texas, 2009) alpha was set at 0.05.

Table 7: Calculation of Sample Size.

Power	Remission rate in Experimental group (control group is 0.1)	N1 (Experimental group)	N2 (control group)	N (total)
0.9	0.7	15	15	30
0.8	0.7	13	13	26
0.75	0.7	12	12	24
0.7	0.7	11	11	22
0.6	0.7	10	10	20
0.9	0.6	21	21	42
0.8	0.6	17	17	34
0.75	0.6	16	16	32
0.7	0.6	15	15	30
0.6	0.6	13	13	26

Safety and tolerability: The following safety measures will be used:

- 1) Collection of vital signs
- 2) Collection of adverse events/side effects. All adverse events including minor rTMS side-effects like post-treatment headache as well as serious and unexpected adverse events like seizure will be recorded. All participants will be encouraged to call or page the PI if they notice any adverse effect or if they are concerned about any medical issues. Side effects will be monitored at each treatment and office visit.

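### Cognitive scores are adjusted for demographics and IQ in a prior regression without arm, with source and visit unstated (0% to about 17% shrinkage), and the IQ test named is not the one in Table 6

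*Combined protocol and SAP*

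**What the plan says.** All of this is in section 6, Study Statistics, of the combined protocol and SAP.

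- **Timing.** Neuropsychological tests are given twice: at baseline and at the 3-month follow-up (taken here as week 16, the last of the three monthly visits).
- **Scaling.** Raw scores are "converted to scaled scores using the cumulative frequency distribution of each measure". The plan does not say whose distribution this is.
- **Adjustment.** "Scaled scores will then be regressed on age, gender, race, years of education, and estimated premorbid IQ", with the IQ estimate taken from the revised NART. Arm is not among the regressors. The next sentence says that education needs no further control, which suggests that the adjusted score is what gets analysed, but the plan does not say so outright.
- **Sources cited.** The two works cited at this sentence are, by their titles in the reference list, normative studies.
- **Battery.** Table 6 gives "Wechsler Test of Adult Reading (WTAR") as the measure of premorbid intelligence. The NART is not listed.
- **Arm comparison.** The secondary-objective analysis applies the same random effects approach to cognition as to the trauma scale, and names the time-by-treatment interaction as a coefficient of interest. The abstract also plans comparisons at individual visits.

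**The concern.** Removing covariates in a first regression that omits arm, and comparing arms in a second, is safe only if the first-step coefficients do not depend on the outcomes being compared. If they are estimated from the trial's own follow-up scores, any chance imbalance in the covariates lets the first step absorb part of the treatment effect. With five covariates and 30 people, chance imbalance is not small.

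The plan can be read in ways that carry this cost and in ways that do not, and nothing fixes the choice before the data are seen. Cognition is a named secondary aim, and this pilot is meant to inform larger studies, so an effect estimate that depends on an unstated scoring choice is a weak planning input.

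Separately, the IQ covariate is tied to a test that the battery does not list.

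**Working it through.** **Inputs from the plan.** N = 30 (Power Analysis: "we have chosen a sample size (N=30) that is feasible"), 15 per arm; five covariates, taken first as one degree of freedom each; two cognitive visits; two-sided 0.05. The plan gives no figure for the cognitive outcomes. Its only design calculation, Table 7, concerns remission. Its ten rows reproduce with a continuity correction (15 per arm for 0.7 against 0.1 at 90% power), but they do not bear on this point.

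**Formula.** Let T be arm, X the p covariates and τ the true effect. If the score is residualised on X alone and the residuals are compared by arm, the expected estimate is τ × (1 − R²), where R² is from regressing T on X. Under randomisation R² averages p/(N − 1).

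- p = 5, N = 30: 5/29 = 17.2%, so the expected ratio is 0.828.
- If race takes two indicators: 6/29 = 20.7%.
- If 24 people are analysed: 5/23 = 21.7%.

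**How the answer depends on the fitting.** If one regression is fitted to both visits, its coefficients average over a visit with no treatment effect and one with it. Half the shrinkage, 17.2%/2 = 8.6%, then appears at follow-up. It cancels from change, because the same covariate term is subtracted at both visits.

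Simulation: 20,000 trials, 15 per arm. Assumptions not in the documents: covariate R² 0.4, within-person residual correlation 0.7, effect 0.6 SD. Entries are estimate divided by true effect; Monte Carlo standard errors are 0.0025 to 0.0037.

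| First-step fitting | Follow-up score | Change (time × treatment) |
|---|---|---|
| In-sample, each visit separately | 0.830 | 0.827 |
| In-sample, both visits pooled | 0.914 | 0.996 |
| In-sample, baseline only | 0.999 | 0.996 |
| Arm and covariates in one model | 1.001 | 0.998 |

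Fixed external norms also give no shrinkage, since their coefficients do not depend on the trial's outcomes.

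**Error rates in the worst case.** With separate fitting at each visit, type I error for change is 0.050. Power for change is 0.65, against 0.75 for unadjusted change, under the assumptions above.

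**Gain from baseline adjustment.** With equal variances σ² at both visits and correlation r, the change contrast has variance proportional to 2σ²(1 − r), and the baseline-adjusted contrast to σ²(1 − r²). The ratio is (1 + r)/2: 0.75 at r = 0.5 and 0.90 at r = 0.8. The documents give no r. This ignores the small cost of estimating the baseline slope at N = 30.

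**The case against.** The strongest reply is that the plan means external norms. Both works cited at the sentence are norms by title, and the sentence reads as a summary of an established scoring procedure. Norm-based scores would produce no shrinkage. This stands as a plausible reading, and it is why the range starts at 0%. It does not settle the matter: the plan never says that norms will be applied, and one cited title covers ages 56 to 97 while the trial enrols adults from 18.

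Four stronger readings are tempting, and the documents support none of them.

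- *The plan shrinks the cognitive effect by 17%.* That needs a fit on the trial sample, done separately at each visit, with residuals as the outcome. None of the three is stated; the scaling is described per measure, not per visit.
- *Aim 2(c) will be reported with too small an effect.* This follows from only some of the readings. For the interaction that the plan names, pooled and baseline-only fitting are unbiased even in-sample.
- *The adjustment cannot be run because the NART is missing.* Table 6 does collect a premorbid-intelligence measure. The documents show a disagreement between text and table, not which entry is the error.
- *Scaling each visit on itself removes change over time.* It would fix the overall mean at each visit, but not the between-arm difference in change, which is what is tested.

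It is also fair to say that even the worst case is modest: there is no false-positive inflation, and only secondary outcomes of a pilot sized for feasibility are affected.

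**Conclusion.** The concern holds as a gap in specification with a bounded cost. The plan adjusts cognitive scores without arm before comparing arms, and does not state the source or visit of that adjustment. Possible shrinkage of the time-by-treatment effect runs from 0% to about 17% (5/29). The upper end assumes in-sample residualising at each visit, one degree of freedom per covariate and all 30 people analysed. For a comparison at the follow-up visit alone, pooled in-sample fitting would cost about 8.6%. The direction is toward the null and the type I error is unchanged.

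The NART/WTAR mismatch is certain from the text and must be reconciled. By itself it is a clarification.

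The main reason to act is that a single model removes the shrinkage under every reading and, for the assumed correlations, is more precise than a change contrast, using data already planned.

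**What to change.** 1. For each cognitive measure, fit one model of the week 16 score on arm, baseline score and the time-since-injury stratum used in randomisation (under 5 years against 5 or more).
2. State the scaling source, either published norms or the trial's baseline distribution, and use the same scaling at both visits.
3. Drop the prior regression. If demographic or IQ adjustment is wanted, enter those covariates in the same model as arm. Choose them sparingly: in the simulation, adding all five to the change model raised the standard error from 0.0026 to 0.0029, a variance ratio of (0.0029/0.0026)² = 1.24.
4. Reconcile the text with Table 6, so that any IQ covariate comes from a test the battery actually gives.

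The cost is analysis wording only, with no new visits or data. The exception is item 4 if the team decides that the NART is the intended test, since it would then have to be added to the battery. Missing week 16 scores can be handled by the multiple imputation already named in the General Description.
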